6.5 Dose escalation and dose modification

Dose escalation is not applicable in this study.

6.5.1 Dose modifications

Dose modifications of the investigational drug are not permitted.

6.5.2 Dose interruptions

For participants who are not able to follow the protocol-specified dosing schedule due to unresolved AEs, or for any other reason cannot attend a visit within a time window specified in [Section 8](#), dose interruptions may be occasionally permitted. A **maximum** of 1 dose of study treatment may be missed in a 3 month period, as specified below. In case of an AE or for any reason (e.g., non-compliance, operational hurdle) resulting in additional interruptions of the dosing scheme, consultation and agreement with Novartis will be necessary to decide whether the participant can continue or needs to be withdrawn from the treatment.

Treatment Period

- No dose interruptions are allowed prior to completion of Week 66 (Day 463): this is a critical period to ensure CD40 occupancy in target tissues

- From Week 68 (Day 477) to Week 108 (Day 757): 1 dose of study treatment may be missed in a 3 month period

These changes must be recorded on the appropriate eCRF.

In all cases the **original visit schedule should be maintained** (no recalculation from the last visit).

6.5.3 Follow-up for toxicities

Participants whose treatment is interrupted or permanently discontinued due to an adverse event or clinically significant laboratory value, must be followed up at least once a week (or more frequently if required by institutional practices, or if clinically indicated) for 4 weeks, and subsequently at approximately 4-week intervals, until resolution or stabilization of the event, whichever comes first. Appropriate clinical experts should be consulted as deemed necessary. All participants must be followed up for adverse events and serious adverse events for 14 weeks following the last dose of CFZ533.

6.6 Additional treatment guidance

6.6.1 Treatment compliance

The site staff will administer the study treatment assigned by IRT to the participants during onsite visits. Kit numbers are collected in the IRT and the site staff will record study drug administration in the eCRF. The compliance will also be assessed by means of site and patient-specific drug accountability by Novartis monitors during site monitoring visits using medication pack numbers, drug label information and information from IRT.

The investigator must promote compliance by instructing the participant to take the study treatment exactly as prescribed and by stating that compliance is necessary for the participant's safety and the validity of the study. The participant must also be instructed to contact the investigator if he/she is unable for any reason to take the study treatment as prescribed. Compliance will be assessed by the Investigator and/or study personnel at each visit based on information provided by the participant. This information should be captured in the source document at each visit. All study treatment dispensed and returned must be recorded in the Drug Accountability Log.

6.6.2 Emergency breaking of assigned treatment code

Emergency code breaks must only be undertaken when it is required to in order to treat the participant safely. Blinding codes may also be broken after a participant discontinues treatment due to disease progression if deemed essential to allow the Investigator to select the participant's next treatment regimen, and after discussion and agreement with the sponsor. Most often, study treatment discontinuation and knowledge of the possible treatment assignments are sufficient to treat a study participant who presents with an emergency condition. Emergency treatment code breaks are performed using the IRT. When the Investigator contacts the system to break a treatment code for a participant, he/she must provide the requested participant identifying information and confirm the necessity to break the treatment code for the participant. The Investigator will then receive details of the investigational drug treatment for the specified

participant and a fax or email confirming this information. The system will automatically inform the Novartis monitor for the site and the study team that the code has been broken. Participants unblinded following an intentional emergency code breaking should be discontinued from the study.

It is the Investigator's responsibility to ensure that there is a dependable procedure in place to allow access to the IRT/code break cards at any time in case of emergency. The Investigator will provide:

- protocol number
- participant number

In addition, oral and written information to the participant must be provided on how to contact his/her backup in cases of emergency, or when he/she is unavailable, to ensure that un-blinding can be performed at any time.

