Premature participant withdrawal	Point/time when the participant exits from the study prior to the planned completion of all study drug administration and/or assessments; at this time all study drug administration is discontinued and no further assessments are planned
Randomization number	A unique identifier assigned to each randomized participant

Screen Failure	A participant who did not meet one or more criteria that were required for participation in the study
Source Data/Document	Source data refers to the initial record, document, or primary location from where data comes. The data source can be a database, a dataset, a spreadsheet or even hard-coded data, such as paper or eSource
Study treatment	Any drug or combination of drugs or intervention administered to the study participants as part of the required study procedures; includes investigational drug(s), control(s) or background therapy
Study treatment discontinuation	When the participant permanently stops taking any of the study drug(s) prior to the defined study treatment completion date (if any) for any reason; may or may not also be the point/time of study discontinuation
Treatment arm/group	A treatment arm/group defines the dose and regimen or the combination, and may consist of 1 or more cohorts.
Variable (or endpoint)	The variable (or endpoint) to be obtained for each participant that is required to address the clinical question. The specification of the variable might include whether the participant experiences an intercurrent event.
Withdrawal of study consent (WoC)	Withdrawal of consent from the study occurs only when a participant does not want to participate in the study any longer and does not allow any further collection of personal data

Amendment 1 (17-Feb-2021)

Amendment rationale

The main purpose of this protocol amendment is to include an additional assessment time point as part of the Interactive Response Technology (IRT) algorithm criteria for participant rollover from the TWINSS core study (CCFZ533B2201) to extension study. ESSDAI and ESSPRI scores at Week 0 may be used for the IRT algorithm in the absence of a score at Week 4 of the core study. This change will allow participants who have missed their ESSDAI (Cohort 1 and Cohort 2) and/or ESSPRI (Cohort 2) assessments at Week 4 to be considered for inclusion in the extension study if these assessments were completed at Week 0 (baseline) of the core study.

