^X Assessment to be recorded in the clinical database or received electronically from a vendor

¹ Corresponds to the Week 60 visit of the core study. Assessments carried out as part of Week 60 as per core study protocol should be used for Week 60E1 of the extension study.

² Optional site visits - Week 66, 70, 74, 78, 82, 86, 90, 94, 98, 102, 106. Participants who are unable to self-administer the PFS injections at home will visit the site and site staff will supervise self-administration or administer the PFS injection for them. Other participants who can self-administer the PFS injection can do so at home at these optional visits.

³ Informed consent should be obtained before commencement of the Week 60 assessments of the core study.

⁴ Contact IRT for new treatment reassignment.

⁵ AEs/SAEs occurring after the participant has signed the informed consent must be captured on the appropriate eCRF page.

⁶ C - These assessments shall be conducted as part of the core study CCFZ533B2201 and will not be repeated in this extension study

⁷ S - Assessment to be recorded in the source documentation only

⁸ [REDACTED]

⁹ Local lab testing of CMV IgG, IgM and DNA (by PCR) must be performed every 3 months until end of study. Hepatitis B monitoring applicable to HBsAg (-) patients who were HBcAb (+) and HBV DNA (-) at screening during the core study. Local lab testing of HBsAg and HBV DNA must be performed every 3 months until end of study.

¹⁰ While on treatment, coagulation monitoring applies only to participants who have antiphospholipid antibodies (lupus anticoagulant, anti-cardiolipin antibodies) and/or who are on pre-existing antithrombotic therapy/prophylaxis, as reflected in the exclusion criteria of the TWINSS core study protocol.

¹¹ Analysis of cryoglobulins will be done only for participants who were positive at screening in the TWINSS core study.

¹² Urine pregnancy tests will be performed throughout the study

¹³ Blood sample is collected pre-dose.

¹⁴ [REDACTED]

¹⁵ [REDACTED]

¹⁶ Optional [REDACTED]

¹⁷ [REDACTED]

¹⁸ [REDACTED]

¹⁹ In case of premature discontinuation, participants will enter the follow-up after completing assessments for this visit.

²⁰ Mandatory to all participants, including those who have discontinued the study prematurely.

²¹ Week 106 is the last dose administration visit in the Treatment Period.

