9.1 Discontinuation and completion

9.1.1 Study treatment discontinuation and study discontinuation

Discontinuation of study treatment for a participant occurs when study treatment is stopped earlier than the protocol planned duration and can be initiated by either the participant or the investigator.

The investigator must discontinue study treatment for a given participant if, he/she believes that continuation would negatively impact the participant's well-being.

Study treatment must be discontinued under the following circumstances:

- Participant/guardian decision
- Pregnancy
- Use of prohibited treatment as per recommendations in the prohibited treatment section
- Any situation in which study participation might result in a safety risk to the participant
- Following emergency unblinding of the treatment arm
- Emergence of the following adverse events:
 - Persistent neutropenia Common Terminology Criteria (CTC) grade 3 or higher
 - SAEs or severe AEs of infection
- Any laboratory abnormalities that in the judgment of the investigator, taking into consideration the participant's overall status, prevents the participant from continuing participation in the study

If discontinuation of study treatment occurs, the investigator should make a reasonable effort to understand the primary reason for the participant's premature discontinuation of study treatment and record this information.

Participants who discontinue study treatment or who decide they do not wish to participate in the study further should NOT be considered withdrawn from the study UNLESS they withdraw their consent (see 'Withdrawal of Informed Consent' section). **Where possible, they should return for the follow-up assessments indicated** in the Assessment Schedule. If they fail to return for these assessments for unknown reasons, every effort (e.g., telephone, e-mail, letter)

should be made to contact the participant/pre-designated contact as specified in the lost to follow-up section. This contact should preferably be done according to the study visit schedule.

If the participant cannot or is unwilling to attend any visit(s), the site staff should maintain regular telephone contact with the participant, or with a person pre-designated by the participant. This telephone contact should preferably be done according to the study visit schedule.

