After study treatment discontinuation, at a minimum, in abbreviated visits, the following data should be collected at clinic visits or via telephone/email contact:

- New / concomitant treatments
- Adverse Events / Serious Adverse Events

The investigator must also contact the IRT to register the participant's discontinuation from study treatment.

If discontinuation occurs because treatment code has been broken, please refer to Emergency breaking of treatment code section ([Section 6.6.2](#)).

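### The protocol contradicts itself on whether an emergency code break ends study participation or only study treatment, and one reading can shorten the TEAE window

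*Protocol*

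**What the plan says.** **On status after a code break.** Protocol 6.6.2 states: "Participants unblinded following an intentional emergency code breaking should be discontinued from the study". Protocol 9.1.1 includes "Following emergency unblinding of the treatment arm" in its list of circumstances in which study treatment must stop. It says that participants who stop treatment "should NOT be considered withdrawn from the study UNLESS they withdraw their consent" and asks that they return for follow-up where possible. It then adds: "If discontinuation occurs because treatment code has been broken, please refer to Emergency breaking of treatment code section", which leads back to 6.6.2.

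**On follow-up.** Protocol 6.5.3 states: "All participants must be followed up for adverse events and serious adverse events for 14 weeks following the last dose of CFZ533". Protocol 10.1.1 (AE monitoring) and 10.1.3 (SAE reporting) use the same 14 weeks. In Table 8-1, footnote 19 sends participants who discontinue prematurely into follow-up, and footnote 20 describes the Week 120/EOS visit as "Mandatory to all participants, including those who have discontinued the study prematurely". Protocol Section 8, however, asks that anyone who discontinues the study early attend as soon as possible for the final-visit assessments.

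**On the analysis.** The adverse event text in SAP 2.4 ends the TEAE window at the earlier of two dates: last dose plus 98 days, or the end of the study period including safety follow-up. SAP 2.1.1.5 derives each subject's study period from the end-of-period visit.

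**The concern.** The two sections give the same event two different consequences, and the cross-reference between them is circular. The difference is not just loose vocabulary. The protocol glossary separates stopping treatment, which may or may not coincide with leaving the study, from premature withdrawal, of which it says: "at this time all study drug administration is discontinued and no further assessments are planned".

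TEAEs and SAEs are part of the primary endpoint. Protocol 4.2 justifies the 14 weeks by the time that plasma concentrations on the 600 mg regimen need to fall to a level with no expected activity. A site that treats the code break as study exit and brings the final visit forward could, under the SAP rule, end that participant's TEAE window well before then.

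Any such loss might also be related to outcome, because 6.6.2 says: "Emergency code breaks must only be undertaken when it is required to in order to treat the participant safely". The tables give crude numbers and percentages of participants, so a person with a shortened window stays in the denominator with no adjustment for the lost time.

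**Working it through.** **Inputs**
- Last dosing visit: Week 106, Day 743 (Protocol Table 8-1 and footnote 21).
- End-of-study visit: Week 120, Day 841 (Protocol Table 8-1 and Section 8 visit windows).
- TEAE window end = min(last dose + 98 days, end of study period) (SAP 2.4, adverse events).
- End of study period is set by the end-of-period visit (SAP 2.1.1.5).
- Maintenance dosing every 14 days (Protocol 4.2).
- Assumption, not in the documents: under a literal reading of 6.6.2 the final visit takes place d days after the last dose, with d between 0 and 14.

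**Step 1: reproduce the plan's figure.** 841 − 743 = 98 days, and 98 / 7 = 14 weeks. This agrees with Protocol 4.2 and 6.5.3 and with the 98 days in the SAP.

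**Step 2: follow each reading through.**

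| Reading | Status after code break | Closing visit | TEAE window ends |
|---|---|---|---|
| 6.6.2 literally, with the early final visit in Section 8 | Out of the study | As soon as possible | At that visit, if it counts as the end-of-period visit |
| 9.1.1 with 6.5.3, 10.1.1, 10.1.3 and footnotes 19 and 20 | Off treatment, still followed | Week 120/EOS | Last dose + 98 days, unless the study period ends sooner |

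Footnote 20 does not say whether the early final visit satisfies the Week 120/EOS requirement, so the first row is not excluded.

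**Step 3: days lost per participant = 98 − d.**
- d = 0: 98 − 0 = 98 days (100%).
- d = 14: 98 − 14 = 84 days (84 / 98 = 86%).
- Follow-up completed, d = 98: 98 − 98 = 0 days.

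If a dose had been missed, or the code were broken later after the last dose, d would be larger and the loss smaller.

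**Step 4: number affected.** The documents give no code-break rate, so no total can be computed. SAP 1.1 reports 206 enrolled, so each affected participant is 1 / 206 = 0.5% of the study.

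**Step 5: which data are exposed.** If an adverse event on treatment prompted the code break, that participant already counts as having a TEAE. What could be missed are later events: further preferred terms, later SAEs or a later death. Scheduled laboratory and vital-sign measurements are less protected than adverse events, because the minimum data set that 9.1.1 asks for after treatment discontinuation covers only new or concomitant treatments and AEs/SAEs.

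**The case against.** The strongest reply is that the protocol requires post-dose safety collection whatever the participant's status. Sections 6.5.3, 10.1.1 and 10.1.3 apply for 14 weeks after the last dose, and footnote 20 expressly provides for someone who has discontinued the study and still owes a Week 120/EOS visit. A site can therefore record study discontinuation under 6.6.2 and go on collecting AEs and SAEs. The glossary phrase about no further assessments defines premature withdrawal, a term that 6.6.2 does not use. The SAP's second limit includes the safety follow-up period and might be read as the whole planned period. All AEs, treatment-emergent or not, are listed in any case.

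Most of this stands, and it rules out three stronger readings that a reader might infer:

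- *That sites cannot comply with all the provisions.* They can, by the route just described.
- *That later SAEs necessarily drop out of the primary endpoint.* They do not if the follow-up provisions are applied.
- *That the loss is concentrated in SAEs and deaths.* The documents do not say so. Section 6.6.2 notes that a code break is usually unnecessary even in an emergency, and it also allows codes to be broken after treatment stops for disease progression.

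The reply does not remove the contradiction between 6.6.2 and 9.1.1. Nor does it prevent an early final visit from being taken as the end-of-period visit under SAP 2.1.1.5. An SAE reported to the safety database after that visit could then appear in the listing but not in the TEAE tables.

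**Conclusion.** The point holds as an internal contradiction of low-to-moderate severity. The documents do not settle whether an emergency code break ends participation or only treatment, and one available reading can end the TEAE window early for a primary safety endpoint.

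The possible loss is 84 to 98 of 98 post-dose days per affected participant if 6.6.2 and the early final visit are applied literally, and 0 days if the follow-up provisions are applied. The upper range rests on two assumptions: exit within 14 days of the last dose, and the early visit counting as the end of that subject's study period.

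The issue is limited in time. Under Protocol 6.4 the extension becomes open-label at final database lock of the core study, after which emergency code breaks no longer arise. The number affected is unknown and probably small.

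**What to change.** **Protocol.** Reconcile 6.6.2, 9.1.1, the early final visit in Section 8 and Table 8-1 footnotes 19 and 20 on whether a code break ends study participation or only study treatment. A single statement should govern AE/SAE and visit data collection after a code break, consistently with the 14-week collection stated elsewhere. It should also say whether an early final visit replaces the Week 120/EOS visit. The treatment decision is for the sponsor's clinicians, and nothing is proposed on it here.

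**SAP.** Add one sentence to the TEAE definition in 2.4 stating how the window ends for a participant whose code was broken.

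**Cost.** One sentence in the protocol or a clarification letter to sites, and one sentence in the SAP. Sample size and the planned summaries are unchanged.

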6.7 Preparation and dispensation

Each study site will be supplied with study drug CFZ533 (iscalimab) and placebo by Novartis, in packaging as described under investigational and control drugs section.

A unique medication number is printed on the study medication label.

Investigator staff will identify the study medication kits to dispense to the participant by contacting the IRT and obtaining the medication number(s). The study medication has a 2-part label (base plus tear-off label), immediately before dispensing the medication kit to the participant, site personnel will detach the outer part of the label from the packaging and affix it to the source document.

As per [Section 4.6](#), during a Public Health emergency as declared by Local or Regional authorities i.e. pandemic, epidemic or natural disaster, that limits or prevents on-site study visits, delivery of IMP directly to a participant's home may be permitted (if allowed by Local or Regional Health Authorities and Ethics Committees as appropriate) in the event the Investigator has decided that an on-site visit by the participant is no longer appropriate or possible, and that it is in the interest of the participant's health to administer the study treatment even without performing an on-site visit. The dispatch of IMP from the site to the participant's home remains under the accountability of the Investigator. Each shipment/provisioning will be for a maximum of 3-month's supply. In this case, regular phone calls or virtual contacts (every 4 weeks or more frequently if needed) will occur between the site and the participant for instructional purposes, safety monitoring, drug accountability, investigation of any adverse events, ensuring participants continue to benefit from treatment and discussion of the participant's health status until the participants can resume visits at the study site.

6.7.1 Handling of study treatment and additional treatment

6.7.1.1 Handling of study treatment

Study treatment must be received by a designated person at the study site, handled and stored safely and properly and kept in a secured location to which only the Investigator and designated site personnel have access. Upon receipt, all study treatment must be stored according to the

instructions specified on the labels and in the IB. Clinical supplies are to be dispensed only in accordance with the protocol. The Investigator should educate the participant on how to properly store the study treatment if the participant is self-administering at home. Technical complaints are to be reported to the respective Novartis Country Organization (CO) Quality Assurance.

The investigational drug iscalimab will be provided in PFS of 300 mg/2mL as a solution for s.c. administration. The matching placebo will be provided in PFS of 0 mg/2 mL as a solution for s.c. administration. Two injections of 2 mL each will be administered to the participant at every dosing visit, as follows:

Loading regimen:

CFZ533 (iscalimab) 600 mg or 300 mg will be administered s.c., weekly for the first 3 doses (Weeks 60E1, 61 and 62); then, from Week 64, iscalimab will be administered s.c. bi-weekly (every other week or Q2W) as described below.

Maintenance regimen:

- **Arm 1 (iscalimab 600 mg):** two 2 mL syringes, each containing 300 mg of iscalimab
- **Arm 2 (iscalimab 300 mg):** one 2 mL syringe of placebo and one 2 mL syringe containing 300 mg of iscalimab

Medication labels will be in the local language and comply with the legal requirements of each country. They will include storage conditions for the study treatment but no information about the participant except for the medication number.

The Investigator must maintain an accurate record of the shipment and dispensing of study treatment in a drug accountability log. Monitoring of drug accountability will be performed by monitors during site visits or remotely and at the completion of the trial. Participants will be asked to return all unused study treatment and packaging at the end of the study or at the time of discontinuation of study treatment.

If local regulations allow, some study participants will be asked to use a Digital Injection Care Management device for disposal of used syringes after home use in a Smart Sharps bin rather than in a standard biohazard sharps bin. This is an optional pilot project that will be conducted at selected countries/sites. The digital box allows to capture the real time date and image of the disposal of the syringe. The connected device/box reminds the participant when medication is due, tracks when medication is taken and interventions as per the Novartis trial protocols. Detailed instructions on use and handling will be described in a separate manual. For the study participants using the Digital Injection Care Management device, there are no risks associated with the disposal of used syringes after home use in the Smart Sharps bin and/or return of the Smart Sharps bin with the used syringes after home use to the study site.

At the conclusion of the study, and as appropriate during the course of the study, the Investigator will return all unused study treatment, packaging, drug labels, and a copy of the completed drug accountability log to the Novartis monitor or to the Novartis address provided in the Investigator folder at each site.

